Baseline visit (week -1): This will coincide with a dialysis day and include obtaining clinical and QOL data, medication list, and a 'Sensewear' physical activity monitor armband will be fitted. 'Senswear' will allow validated measurement of free living physical activity over a 7 day period^{70, 71}.

Randomisation visit (week 0): This visit will occur on a non-dialysis day, during a short inter-dialytic interval and at least 12 hours after the last dialysis session. The visit will include an echocardiogram, bioelectrical impedance, CPEX with lung function test, applanation tonometry, flow mediated vascular dilatation, measurement of muscle strength and blood sampling for routine tests and for future testing of novel serum markers. Outcomes assessors will be blinded to the group allocation of the patient.

Participants will be randomised to one of 3 groups: 1) the intra-dialytic LF-EMS group, 2) the dynamic intra-dialytic exercise group or 3) the usual care without any dynamic exercise or LF-EMS group.

Treatment – familiarisation period (week 0-3): Exercise under close instruction and supervision will be commenced in patients randomised to either of the exercise groups. Over the initial 3 weeks, LF-EMS and dynamic exercise duration will be gradually increased to 30 mins per dialysis session. Previous work has indicated that 3 weeks of regular LF-EMS exposure is required to achieve an intensity that will elicit a cardiovascular training stimulus ⁷² (i.e. 40-60% VO₂ reserve⁷³). LF-EMS intensity will be gradually increased, as tolerated, with the aim of achieving the appropriate level by week 3. Dynamic exercise work load will be gradually increased to achieve a heart rate and workload equivalent to that achieved at 40-60% VO₂ reserve during baseline CPEX. As the use of heart rate during dialysis may not always provide an accurate reflection of workload⁷³, rating of perceived exertion (RPE) will also be used to monitor exercise intensity in both groups⁷².

Graded LF-EMS test (week 3): to ensure that LF-EMS tolerance has improved to a level that elicits a workload of 40-60% VO₂ reserve, a graded LF-EMS test will be performed in this group following the 3 week familiarisation period. This will be performed during a dialysis session. Stimulation intensity will be incrementally increased every 5 minutes until the tolerable level is achieved⁷² and oxygen consumption measured with the respiratory gas analysis system.

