Treatment visit (weeks 3-12): Patients in the exercise groups will progress from 30-45 mins of exercise at an intensity of 40-60% VO₂ reserve as regulated by heart rate and RPE. Where this isn't possible, maximal tolerated exercise intensity will be continued.

Treatment completion visit (week 13): This visit will occur on a non-dialysis day, during a short interdialytic interval and at least 12 hours after last dialysis session. The visit will include recording of any clinical events, QOL assessment, free living with 'Senswear' for the following 7 days, echocardiogram, bioelectrical impedance, CPEX with lung function test, applanation tonometry, flow mediated vascular dilatation, measurement of muscle strength and blood sampling for routine tests and for future testing of novel serum markers. Outcomes assessors will be blinded to the group allocation of the patient.

Exercise training and EMS in kidney disease Page 7 of 17 Version 1 - 07.11.2013

Wash out and study completion visit (week 20): This part of the study will only be performed, if further funding can be obtained. This visit will occur on a non-dialysis day, during a short inter-dialytic interval and at least 12 hours after last dialysis session. The visit will include recording of any clinical events, QOL assessment and free living physical activity with 'Senswear' for the following 7 days, echocardiogram, bioelectrical impedance, CPEX with lung function test, applanation tonometry, flow mediated vascular dilatation, measurement of muscle strength and blood sampling for routine tests and for future testing of novel serum markers. During the 8 week 'washout' period, patients will undertake usual care which will not involve dynamic exercise training or LF-EMS.

Randomisation: Stratified permuted block randomisation with a variable block size (sizes 3 and 6 used) will be employed. Stratification variables are age (young, middle-aged, old) and gender (male, female), and a separate permuted block randomisation will be performed within each of the six strata. The randomisation list will be created and held by a Warwick Medical School statistician who the study team are going to contact to obtain the group allocation of a recruited patient. The randomisation list will not be made available to the study team.

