The two primary objectives of this study are to generate estimates, in particular variance estimates, for a sample size calculation of a subsequent fully powered RCT and to determine the likelihood of a successful conduct of such an RCT. The latter will be assessed by estimating recruitment and drop-out rate indication feasibility of a large-scale trial. Since this study is a pilot the statistical analysis will be primarily descriptive. Point estimates and corresponding 95% confidence intervals will be calculated for all outcome measures in the three arms and the aforementioned rates. Furthermore the distribution of outcome measures will be assessed to identify appropriate statistical analysis methods for a future RCT. Between group comparisons via statistical tests (unpaired two-sample t-test for continuous outcomes, Chi-squared tests for categorical (binary) outcomes) will be conducted, however, it will be clearly stated that these yield only preliminary results since the study is not powered for such investigations. The results of these tests will only be used to identify overwhelming evidence of inferiority of the two experimental treatments relative to usual care so that plans of a full trial can be abandoned or an arm dropped. In accordance with Kieser and Wassmer (1996), the upper 90% confidence limit will be chosen as the estimate of the variance of the treatment effect for a future trial's sample size calculation. Intention-to-treat and per protocol analyses will both be conducted to determine potential ranges of results.

References:

- 1. NICE. Guideline CG73 Chronic KIdney Disease.
- 3. System URD. USRD 2006 annual data report Bethesda, MD: National Institutes of Health, National Institute of Diabetes and Digestive and Kidney Diseases, 2006.

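### The repeated continuous measures are compared by an unadjusted t-test, so baseline values and the randomisation strata go unused, and no baseline-adjusted variance is planned for sizing the full RCT

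*Protocol*

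**What the plan says.** Protocol, Statistical analyses, names the between-group tests: "unpaired two-sample t-test for continuous outcomes, Chi-squared tests for categorical (binary) outcomes". It mentions no covariate or stratum, and does not say whether the t-test is applied to week-13 values or to changes from baseline.

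The design supplies the information that this test leaves out:

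- Randomisation: "Stratification variables are age (young, middle-aged, old) and gender (male, female"), with separate permuted blocks in each of the six strata.
- Baseline visit (week -1): "This will coincide with a dialysis day and include obtaining clinical and QOL data, medication list".
- Randomisation visit (week 0): echocardiography, CPEX, tonometry, FMD, muscle strength and bloods. Treatment completion visit (week 13) repeats these and QOL.

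On purpose, Statistical analyses states: "The two primary objectives of this study are to generate estimates, in particular variance estimates", intended for sizing a later trial. It adds that "the upper 90% confidence limit will be chosen as the estimate of the variance of the treatment effect" for that calculation, without naming the model that yields it. The tests have a restricted role: "The results of these tests will only be used to identify overwhelming evidence of inferiority of the two experimental treatments relative to usual care", after which the full trial may be given up or an arm removed. The analysis method of the later trial is left open: "the distribution of outcome measures will be assessed to identify appropriate statistical analysis methods for a future RCT".

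**The concern.** When a patient's starting value predicts the final value, a comparison that ignores it leaves explainable variation in the error term. Likewise, if age group and gender predict outcome, stratifying on them and then analysing as if allocation were simple gives standard errors that are on average too large.

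Two things are at stake. First, the between-arm comparisons inform a decision to abandon the programme or drop an arm, and each arm will have only about 24 evaluable patients. Second, the pilot exists largely to deliver a variance. If the later trial adjusts for baseline, it needs the residual variance or the baseline/week-13 correlation, and neither is among the planned outputs.

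**Working it through.** **Plan's own figure.** Sample size calculation gives 30 per group after 20% drop-out, aiming at 20 to 25 evaluable. 24/(1 - 0.20) = 30, and 30 × 0.80 = 24, so the figure reproduces. I use 24 evaluable per arm.

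**Assumptions (not in the protocol).** The correlation rho between baseline and week 13 is taken as 0.5, 0.7 and 0.8. The SD is the same at both times, set to 1. For illustration: two-sided 5% level, 80% power for the full trial, true difference 0.5 SD. The 90% limit is read as one-sided.

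**Variance V, relative to the week-13 value**

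- t-test on week-13 values: 1
- t-test on changes: 2(1 - rho)
- ANCOVA: 1 - rho²
- ANCOVA relative to change scores: (1 - rho²)/[2(1 - rho)] = (1 + rho)/2

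The half-width of an interval for the difference scales with the square root of these ratios.

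| rho | ANCOVA vs week-13 t-test | half-width shorter by | ANCOVA vs change t-test | half-width shorter by |
|---|---|---|---|---|
| 0.5 | 0.75 | 13% | 0.75 | 13% |
| 0.7 | 0.51 | 29% | 0.85 | 8% |
| 0.8 | 0.36 | 40% | 0.90 | 5% |

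A simulation with two arms of 24 and normal data, which includes the cost of estimating the slope, gave ratios of ANCOVA to week-13 t-test of 0.77 at rho 0.5 and 0.52 at rho 0.7. At rho 0 the ratio was 1.02, so adjustment costs about 2% if baseline is useless.

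**Power in the pilot** for a 0.5 SD difference: Φ(0.5 × √(24/(2V)) - 1.96). For example, V = 1 gives Φ(1.732 - 1.96) = 41%.

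| rho | week-13 t-test | change t-test | ANCOVA |
|---|---|---|---|
| 0.5 | 41% | 41% | 52% |
| 0.7 | 41% | 61% | 68% |
| 0.8 | 41% | 78% | 82% |

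**Full-trial size per arm:** 2 × (1.960 + 0.842)² × f × V / 0.5², where f = df/χ²(0.10, df) is the upper-limit factor. For two arms, f is 1.344 at 46 df (t-test) and 1.349 at 45 df (with baseline).

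| rho | from week-13 variance | from change variance | from ANCOVA variance |
|---|---|---|---|
| 0.5 | 85 | 85 | 64 |
| 0.7 | 85 | 51 | 44 |
| 0.8 | 85 | 34 | 31 |

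Charging five further degrees of freedom for the six strata (40 df, f = 1.377) raises the ANCOVA figures by one per arm, to 65, 45 and 32.

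If a trial analysed by ANCOVA were sized on the unadjusted variance, the excess is the reciprocal of the variance ratio: 1.33, 1.96 and 2.78 for week-13 values, or 1.33, 1.18 and 1.11 for changes.

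**Age and gender.** The protocol gives no figure for how far these predict any outcome, so the additional gain cannot be computed.

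**The case against.** The strongest reply is that this is a pilot whose analysis is declared mainly descriptive, with tests labelled preliminary and confined to detecting clear inferiority. Ignoring prognostic strata makes a test conservative, not invalid. Covariate details often sit in an SAP, which is not shown. The intervals promised are per arm, and ANCOVA of a difference does not bear on those.

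Much of this stands: it makes the point one of efficiency. But the protocol names the test, so this is a choice already made, and its result can end the programme.

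Three stronger readings are tempting and are not supported.

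- A reader might infer that every outcome has a baseline. Tolerability, acceptance, adherence, recruitment and drop-out cannot have one, and no baseline time is given for the Malnutrition-Inflammation Score.
- A reader might infer that the t-test inflates the variance carried forward. The protocol does not link the two. It restricts the tests to the inferiority check and names no model for the carried variance.
- A reader might infer that the full RCT will be oversized, perhaps nearly threefold. That requires a future baseline-adjusted analysis, which is left open, and a comparison of week-13 values. Outcome measures speaks of improvement, which may mean change scores. If the later trial is analysed unadjusted on the same scale, the unadjusted variance is the right input.

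**Conclusion.** The point holds for the continuous measures taken at week -1 or 0 and repeated at week 13. The named test is valid but uses neither covariate adjustment for baseline nor the strata, and the plan provides no baseline-adjusted residual variance for its own primary objective.

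The loss is real whenever baseline predicts outcome, but its size cannot be fixed from the protocol. Over rho 0.5 to 0.8, intervals for the between-arm difference could be 13% to 40% shorter than with week-13 values, or 13% to 5% shorter than with change scores. On either scale ANCOVA is at least as precise, apart from a trivial cost in degrees of freedom. Oversizing of the full RCT is conditional on a mismatch between the variance used and the analysis planned.

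**What to change.** For the repeated continuous measures, replace the t-test in Statistical analyses with ANCOVA of the week-13 value on arm, baseline value, age group and gender, fitted to all three arms. Report:

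- adjusted between-arm differences with 95% confidence intervals;
- the residual variance with its upper 90% limit;
- the raw SD and the baseline/week-13 correlation.

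Add that the full RCT will be sized on the variance that matches its planned analysis. With the raw SD and the correlation both reported, that choice can still be made later.

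Cost: a short protocol change and no new data. With 24 per arm, a three-arm model has 72 - 3 = 69 residual degrees of freedom. Baseline (1), age group (2) and gender (1) reduce this to 65. The upper-limit factor is 1.267 at 69 df and 1.283 at 63 df (baseline plus five stratum indicators), so at 65 df it lies between the two.

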Sample size calculation: Since this is a pilot study, no formal sample size calculation was conducted. The sample size was chosen based on Kieser and Wassmer (1996), who recommended recruiting 20 to 25 patients per group for a pilot study (with a normally distributed outcome) where the aim is to minimise the overall sample size of pilot and large scale RCT. Being conservative, a drop-out rate of 20% is assumed and thus a sample size of 30 patients per group has been chosen.

Dynamic exercise and electrical muscle stimulation treatment intervention

Low frequency electrical stimulation (LF-EMS) (treatment group): Bilateral neoprene straps will be applied to the quadriceps and hamstrings 3 times per week during the second hour of dialysis. Rhythmical contractions will occur at a frequency of 3-4 Hz. Participants will be introduced to the EMS protocol very gradually to ensure tolerance and adherence. On the first occasion the straps will be activated for 5 minutes at a very light current amplitude (milliamps, mA) (less than visible contraction), so that participants can become accustomed to the unusual sensation. During the following 8 familiarisation sessions (3 weeks), duration will be incrementally increased to 30 mins and intensity increased as tolerated. By the end of the third week the intention is that the patient will be accustomed to using the straps for 30 mins at an intensity equivalent to 40-60% VO2 reserve⁷². This will be assessed with an intradialytic graded LF-EMS CPEX (as above). During LF-EMS sessions, exercise intensity will be regulated using a combination of heart rate and rating of perceived exertion (RPE). Intensity will be further increased over the 9 week period of the intervention to the maximum tolerated level. This is necessary to ensure that, whilst cardiovascular reserve and skeletal muscle function improve, intensity remains at a level that will elicit a cardiovascular exercise response. Duration will also be increased to 45 mins by the second week of the intervention and will remain at this level throughout. Each session will be preceded by a 10 minute 'ramp-up' period during which intensity will be gradually increased to the training level⁷². Each session will be concluded with a 5 minute cool-down at a gradually reducing intensity. The LF-EMS units will record the intensity and duration of the stimulation which can be downloaded for analysis.

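### The rule for sizing the future trial names the variance of the treatment effect, where a two-sample t-test calculation needs the within-arm variance of the outcome

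*Protocol*

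**What the plan says.** The Statistical analyses section of the protocol opens by naming two main goals, of which one is "to generate estimates, in particular variance estimates, for a sample size calculation of a subsequent fully powered RCT"; the other is to judge whether such a trial could be run. For the variance objective the section fixes one rule, attributed to a cited methodological paper: "the upper 90% confidence limit will be chosen as the estimate of the variance of the treatment effect", and that figure then enters the sizing of the full trial.

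The same section plans an "unpaired two-sample t-test for continuous outcomes" for comparing groups. The only other interval level it names is 95%, for the outcome estimates in each arm and for the recruitment and drop-out rates.

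The Sample size calculation paragraph relies on the same paper for a pilot of 20 to 25 patients per group with a normally distributed outcome. It assumes 20% drop-out and settles on 30 per group.

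**The concern.** Two different variances are involved. One is the spread of the outcome between patients within an arm, σ², a property of the population and of the measurement. The other is the sampling variance of the estimated difference between two arms, which shrinks as the pilot grows. A sample-size formula for two means takes the first, because it works out for itself how the second will fall with the future n. Supplying the second divides by a sample size twice.

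The rule names the second. The figure it governs is the deliverable of a stated primary objective, so an analysis plan or report that followed the sentence faithfully would carry a variance far too small into the design of the full trial. A lesser gap is that an upper 90% limit may be a one-sided limit or the upper end of a two-sided 90% interval, and the sentence does not say which.

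**Working it through.** **Inputs from the protocol.** 30 per group, 20% drop-out and a cited range of 20 to 25 per group (Sample size calculation); three arms, with equal allocation implied by block sizes of 3 and 6 (Randomisation); unpaired t-test and upper 90% limit (Statistical analyses).

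**Assumptions, for illustration only.** The protocol gives no alpha, power, effect size or SD for the future trial. I take two-sided alpha 0.05, 80% power, a true difference of 0.5 SD (0.3 SD as a second case), and a pilot SD equal to the true SD.

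**1. The protocol's own figure.** 24/(1 − 0.20) = 30 exactly, so 30 per group leaves 30 × 0.8 = 24 evaluable, inside the cited 20 to 25. The ends of that range give 20/0.8 = 25 and 25/0.8 = 31.25, rounded up to 32. The pilot size is consistent with its inputs.

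**2. The quantity named.** Variance of the estimated difference = σ²(1/n1 + 1/n2).
- 24 evaluable per arm: σ²(1/24 + 1/24) = σ²/12.
- 30 evaluable per arm: σ²(1/30 + 1/30) = σ²/15.

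**3. The upper limit as a multiple of s².** The multiplier is df/χ²(q, df), with q = 0.10 for a one-sided 90% limit and q = 0.05 for the upper end of a two-sided 90% interval, at 24 evaluable per arm:

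| Arms pooled | df | One-sided | Two-sided, upper end | Ratio |
|---|---|---|---|---|
| Two | 46 | 1.344 | 1.463 | 1.088 |
| Three | 69 | 1.267 | 1.356 | 1.070 |

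**4. Future n per arm.** n = 2(1.960 + 0.842)² × V/δ², where V is the variance supplied in units of σ² and δ is the difference in SD units. For δ = 0.5 this is about 62.8 × V.

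- True variance, V = 1: n = 63.
- Limit on the outcome variance, two arms: V = 1.344 gives 85; V = 1.463 gives 92.
- Limit on the outcome variance, three arms: V = 1.267 gives 80; V = 1.356 gives 86.
- Literal rule, 24 evaluable per arm: V = 1.344/12 = 0.112 or 1.463/12 = 0.122; both give 8.
- Literal rule, 30 evaluable per arm: n = 6 with either limit.

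This is the normal-approximation formula. Allowing for the t distribution adds about one patient (64 and 9 in place of 63 and 8).

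**5. Real power at the literal n.** Power ≈ Φ(δ√(n/2) − 1.96). At n = 8 and δ = 0.5 this is Φ(1.00 − 1.96), about 17%; at n = 6 it is about 14%. For δ = 0.3 with 24 evaluable per arm, the literal rule gives 20 to 22 per arm against 175 needed, with power of about 16 to 17%.

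**The case against.** The strongest reply is that nobody would apply the sentence literally. The section says twice that the variance is wanted for a sample-size calculation, it ties the rule to a named method, and the planned comparison is a t-test whose formula takes the outcome variance. The literal answer would also give itself away: 6 to 8 patients per arm for a fully powered trial is below the pilot's own 30. This largely stands. It lowers the practical risk, but it does not make the sentence right, and the protocol has chosen to fix this rule itself.

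The cited paper may settle whether the limit is one-sided, and that is the more natural reading of the phrase. The paper is not at hand, so nothing here rests on it.

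A reader might infer more than the document supports:

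- *That the future trial will be undersized twelvefold.* That follows only from the literal reading, which the context argues against.
- *That analysts will differ by 15%.* That figure (1.463/1.267 = 1.15) combines the sidedness with a choice between two and three arms. How arms are pooled is ordinary detail for a statistical analysis plan. Sidedness alone accounts for 7 to 9%.
- *That the rule fails for skewed markers such as CRP or NT-pro-BNP.* The normality remark qualifies the recommended pilot size, those markers are not in the primary outcome, the section already plans to assess distributions, and any loss of coverage would rest on assumed shapes.
- *That an ANCOVA residual variance is required.* The protocol plans an unpaired t-test, for which the unadjusted within-arm variance is the matching input.

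**Conclusion.** The rule is wrong as written, and the defect is minor. It names a variance that is smaller than the one needed by a factor of 12 at 24 evaluable patients per arm (15 at 30). Under the stated assumptions, literal use would turn a requirement of 63 per arm into about 8, with real power near 17%. The probable intention was the outcome variance. On that reading, what remains is the unstated sidedness, worth 9% of the future sample size with two arms pooled and 7% with three.

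The factors of 12 and 15 follow from the protocol's own numbers. The sample sizes and powers depend on the assumed alpha, power, effect size and SD. The pilot's size, conduct and group comparisons are not affected, and the right variance can be computed from the same data at any time.

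**What to change.** In Statistical analyses, replace the reference to the variance of the treatment effect with:

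> the one-sided upper 90% confidence limit of the within-arm variance of the outcome, pooled across arms, on the scale and with the adjustment planned for the future trial's analysis

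If the upper end of a two-sided 90% interval was meant, say that instead; what matters is that one is stated. The closing words keep the carried-forward variance matched to the future analysis: unadjusted for a t-test, residual for an adjusted model with its own degrees of freedom. Pooling assumes similar variances in the exercise and usual-care arms, which the per-arm estimates will allow to be checked.

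The cost is one phrase. No data collection, sample size or other analysis changes.
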